4.7.5 Independent Adjudication Committee

4.7.5.1 Cardiovascular Clinical Event Committee (CCEC)

A Cardiovascular Clinical Event Committee (CCEC), blinded to the treatment of the subjects, will independently adjudicate certain cardiovascular adverse events, and they will operate in accordance with a dedicated Clinical Event Committee Charter/Manual of Operations: Dapagliflozin Program.

Events related to the following will be sent to the CCEC for adjudication:

Death including:

- (a) Cardiovascular Death
- (b) Non-cardiovascular Death

Myocardial Infarction (MI) including:

- (a) ECG and /or cardiac enzymes confirmed MI
- (b) Sudden death
- (c) PCI-related myocardial infarction
- (d) CABG-related myocardial infarction
- (e) MI diagnosed via pathologic criteria
- (f) Silent MI

Fatal and Non-fatal Stroke including:

- (a) Ischemic stroke
- (b) Hemorrhagic stroke

Serious Adverse Events of the following:

- (a) Heart failure
- (b) Cardiac arrhythmia
- (c) Unstable angina
- (d) Unplanned arterial revascularization (coronary, carotid and peripheral)
- (e) Cardiac arrest with successful resuscitation
- (f) Deep Vein Thrombosis and Pulmonary Emboli
- (g) Systemic non-stroke arterial embolism/thrombosis including systemic arterial occlusion
- (h) Non-traumatic amputation of the lower limb. Only events above the ankle will be considered for adjudication.

In order to provide the independent CCEC with appropriate and adequate information for adjudication of the listed events, please consult the Reference Manual, Dapagliflozin Cardiovascular Adjudication Reference Manual for Primary Investigators and Study Staff.

4.7.5.2 Hepatic Adjudication Committee

An independent Hepatic Adjudication Committee, blinded to the treatment of the subjects, will determine the probability that drug-induced liver injury (DILI) is the cause of liver-related abnormalities, including, but not limited to:

- Hepatic disorders leading to discontinuation from study treatment and/or death
- Liver laboratory abnormalities such as elevated AST and/or ALT with or without TB elevations.

A separate Adjudication Manual will define and describe the procedure for the handling, reporting and classification of these cases.

4.8 Volume of blood sampling and handling of biological samples

The total volume of blood that will be drawn from each subject in this study is as follows:

Table 7 Volume of blood to be drawn from each subject

Assessment		Sample volume (mL)	No. of samples	Total volume (mL)
Safety	Clinical chemistry	15	18	270
	Haematology	5	18	90
Pharmacokinetic		3	6	18
Total		23	24	378
Genotyping		9	1	9

4.8.1 Analysis of biological samples

4.8.1.1 Clinical chemistry samples

The analytic stability limits defined by the contracted central clinical laboratory will be applied to all analyses performed on behalf of AstraZeneca. The central laboratory will not analyse samples that fall outside these stability limits. Analytical data will not be reported if found to have been derived from a sample that fell outside these stability limits. The standards of procedure followed by the central laboratory may be amended in accordance with its Standard Operating Procedures. The central laboratory will inform AstraZeneca of the stability limits relevant to this study before the first patient gives informed consent to take part in the study.

If the contracted central clinical laboratory chooses to sub-contract the analytical work to another laboratory, the contracted central clinical laboratory must assure itself and provide assurance to AstraZeneca that the other laboratory will apply defined stability limits to all analyses performed on behalf of AstraZeneca. Samples falling outside these limits must not be analysed or data reported. The other laboratory will inform AstraZeneca of the stability limits relevant to this study before the first patient gives informed consent to take part in the study.

4.9 Genetic measurements and co-variables

Patients who provide written informed consent related to genetic research will provide a blood sample according to the Study Plan, see [Table 1](#). Individual patients will not be identified. Samples and data will be kept confidential and stored separately. For more information, see [Appendix F](#).

5. DATA MANAGEMENT

Data must be entered into the WBDC system at the investigational centre within 2 business days after the scheduled visit (except for SAEs that should be entered within 1 calendar day). Trained study personnel will be responsible for entering data into the WBDC system according to the Instructions for the Investigator including the data entry instructions. Data includes observations, tests and assessments specified in the protocol. Data entered in the WBDC system will immediately be saved at a central database and changes tracked to provide an audit trail. When data have been entered, reviewed, edited and Source Data Verification (SDV) performed, the Investigator will electronically sign the eCRF and the data will be locked to prevent further editing. An electronic copy (disc or equivalent) of the eCRF will be provided to the investigational centre after the study database has been locked for archiving at the investigational centre.

Data from the central laboratory assessments will be either loaded into WBDC or returned to AstraZeneca directly as datasets, and validated to ensure that it is consistent with the clinical data. Any queries on the data will be raised and resolved within the WBDC system or other designated systems. If loaded to WBDC efficacy variables will be blinded to investigator according to section 4.6.

Data verification and validation will be performed. The Investigator should answer any external queries raised by AstraZeneca in a timely manner, and query resolutions will be saved in the central database. Prior to breaking the treatment codes, all decisions on the evaluability of the data from each individual patient must have been made and documented. The Study Delivery Team at AstraZeneca will document the date of clean file and database lock.

The Study Data Management Plan will describe in greater detail the methods used to collect, check, and process clinical data. It will also clarify the roles and responsibilities of the various functions and personnel involved in the data management process.

Following database lock, required amendments to the database due to critical errors will only be allowed with the appropriate supporting documentation. Non-critical errors will not result in amendments to the database but will be captured via the appropriate documentation. An electronic copy (disc or equivalent) of the eCRF will be made available to the Investigator centre after the study database has been locked.

Concomitant medications will be coded using the Bristol-Myers Squibb Drug Dictionary. Adverse events will be coded using MedDRA.

6. STATISTICAL METHODS AND DETERMINATION OF SAMPLE SIZE

6.1 Statistical evaluation – general aspects

A comprehensive Statistical Analysis Plan (SAP) will be prepared before unblinding of the data.

The first 24 weeks of double-blind treatment represent the confirmatory part of the study. Efficacy and safety data of the first 24-week treatment period will be analyzed after completion of this treatment period. Efficacy and safety analyses for the long-term double-blind extension period I and II will be performed for exploratory purposes and will provide supportive data. All investigators, patients and staff of Bristol-Myers Squibb and AstraZeneca except drug safety department and IPS will be blinded until completion of the 24-week treatment period (see Sections 3.6.1 and 3.6.2). During the long-term double-blind extension period I and II, all investigators, patients, and study monitors will remain blinded.

6.2 Description of outcome variables in relation to objectives and hypotheses

The primary objective of the study is to assess the efficacy of 2.5 mg, 5 mg and 10 mg dapagliflozin compared to placebo as add-on therapy to insulin in improving glycaemic control in subjects with type 2 diabetes who have inadequate glycaemic control on ≥ 30 IU injectable insulin daily for at least 8 weeks prior to enrolment, as determined by the change in HbA1c levels from baseline to week 24. The objective will be statistically analyzed using Dunnett's method (overall type I error rate for the primary endpoint 0.05). The significance level for each pair-wise group comparison of dapagliflozin versus placebo will be approximately 0.019.

Key secondary objectives are to compare the effects of each dose of dapagliflozin versus placebo given as add-on therapy to insulin after a 24-week double-blind treatment period by evaluation of:

1. The change in body weight from baseline to week 24
2. The absolute change in calculated mean daily insulin dose from baseline to week 24
3. The proportion of subjects with calculated mean daily insulin dose reduction from baseline to week 24

4. The change in FPG from baseline to week 24

The statistical testing of the primary and key secondary outcome variables will proceed in a sequential manner, to control the type I error rate within each dapagliflozin group at the 0.05 level. Specifically, the significance or non-significance of the treatment comparisons for the primary outcome variable will determine which, if any, statistical inferences are made for the key secondary outcome variables. Only those dapagliflozin groups significantly superior to placebo for the primary outcome variable will have statistical inference versus placebo for the first key secondary outcome variable, (1). Then, the testing for the other key secondary outcome variables will proceed so that

- the significance or non-significance of the treatment comparisons for (1) will determine which, if any, statistical inferences are made in treatment comparisons for (2), and
- the significance or non-significance of the treatment comparisons for (2) will determine which, if any, statistical inferences are made in treatment comparisons for (3), and
- the significance or non-significance of the treatment comparisons for (3) will determine which, if any, statistical inferences are made in treatment comparisons for (4).

If at least one of the primary comparisons between a dapagliflozin treatment group and the placebo treatment group is significant at the 0.019 level for the primary outcome variable, all statistical tests for the four key secondary outcome variables will be performed and nominal p-values will be reported. However, in order to protect the global type I error rate of the hierarchical testing procedure, the interpretation of the statistical significance of treatment comparisons for each secondary outcome variable will be done using a step-wise procedure.

Other secondary outcome variables shall provide supportive efficacy and safety information regarding the differences between the treatment groups.

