6.5 Determination of sample size

Each pairwise treatment group comparison will be tested at a significance level of approximately 0.019, according to Dunnett's method, in order to maintain an overall type I error rate < 0.050 for the primary objective. To detect a difference of 0.5% between each dapagliflozin group versus placebo for changes from baseline to week 24 in HbA1c, assuming a SD = 1.2%, and at a two-sided significance level of 0.019, 153 evaluable subjects are needed in each treatment group to provide 90% power. Assuming that 5% of the subjects will not be evaluable in the full analysis set, 161 subjects per treatment group (644 subjects total) are planned for randomization.

Approximately 700 patients will be offered to enter the long-term extension period II. This estimate is based on the number of actually randomised patients (808) and the assumption that approximately 14 % of the randomised patients will have been withdrawn at week 48 (visit 12).

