4. RECENTLY COMPLETED STUDIES

An additional phase 2b study (MB102009) has been completed and two Phase 3 studies (MB102013 and MB 102 014) short-term treatment periods have been concluded but not yet reported. Thus, the results from these studies are preliminary.

MB102009 was conducted in subjects who were not controlled on combination antihyperglycemic therapy with metformin and/or TZD and subcutaneous insulin. A total of 75 subjects were treated with dapagliflozin (10 or 20 mg) or placebo plus metformin and/or TZD and insulin for a treatment period of 12 weeks. The safety data from this recently completed study are in line with data from previously reported studies and indicate that the combination of dapagliflozin (in doses of 10 mg and 20 mg) and insulin is safe and well tolerated. Please note that 10 mg is the top dose of dapagliflozin being tested in phase III program.

Study MB102013 is a Phase III study evaluating the efficacy and safety of dapagliflozin compared to placebo in drug-naïve type 2 diabetic patients. The short-term treatment period was 24 weeks and is followed by an ongoing 78-week double-blind extension period. The main cohort of the study has 7 arms (placebo, 2.5, 5 and 10 mg dapagliflozin with morning (am) dosing and 2.5, 5 and 10 mg dapagliflozin with evening (pm) dosing), including patients with baseline HbA1c ≥ 7.0 - $\leq 10.0\%$. A statistically significant effect of dapagliflozin on HbA1c after a 24-week treatment period was observed for the 5 and 10 mg dapagliflozin groups versus placebo. Overall, the safety profile was consistent with previous studies conducted with dapagliflozin. ALT elevations $>3xULN$ were observed in 6/402 (1.5%) dapagliflozin patients including one subject with ALT $>5xULN$ compared to 0/75 in the placebo group. All of these elevations were transient and none was associated with total bilirubin $>1.5 X ULN$ or hepatic failure. The importance of this is unclear and requires further data to elucidate.

Study MB102014 is a Phase III study evaluating the efficacy and safety of dapagliflozin plus metformin compared to placebo plus metformin in type 2 diabetic patients with baseline HbA1c of 7-10%. The short-term period was 24 weeks followed by an ongoing 78-week double-blind extension period. The study includes 3 dapagliflozin + metformin treatment groups; 2.5, 5 and 10 mg. A statistically significant effect of dapagliflozin on HbA1c after a

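### The primary HbA1c comparisons use single-step Dunnett; step-down Dunnett would keep the 5% family-wise error and raise power at no cost in patients (an efficiency gain, not an error)

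*Protocol*

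**What the plan says.** Protocol section 6.2 names Dunnett's method for the primary objective, with "overall type I error rate for the primary endpoint 0.05", and continues: "The significance level for each pair-wise group comparison of dapagliflozin versus placebo will be approximately 0.019". The sample-size section (6.5) agrees: "Each pairwise treatment group comparison will be tested at a significance level of approximately 0.019, according to Dunnett's method". The purpose given there is control over the whole primary family, namely "in order to maintain an overall type I error rate < 0.050 for the primary objective". It sizes the trial "at a two-sided significance level of 0.019", for a difference of 0.5 with SD 1.2, and concludes that "153 evaluable subjects are needed in each treatment group to provide 90% power". The synopsis repeats this.

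One level therefore applies to all three doses, whatever happens to the other two. No step-down is described. Later in 6.2, the sentence on when the key secondary tests are run refers to a primary comparison that "is significant at the 0.019 level for the primary outcome variable", this time without the word approximately.

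Two other provisions bear on the point. Under 6.2, only a dose that is superior on HbA1c goes on to body weight, then absolute insulin dose, then the proportion with insulin reduction, then FPG, with error control claimed at 0.05 within each dose. Under 6.4.1, treatment differences are reported with ordinary two-sided 95% confidence intervals.

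**The concern.** In single-step Dunnett, the second and third doses must clear the three-comparison threshold even after stronger doses have been declared effective. Closing the Dunnett family over the three doses gives the step-down form, which relaxes the threshold as hypotheses are rejected and still controls the family-wise error strongly. The usual reason to prefer single-step is that it has matching simultaneous confidence intervals. This plan does not report them, so it gives up power without that return.

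What is at stake is more than one p-value per dose. The HbA1c test is the gate to the four key secondary endpoints, so a dose that narrowly misses loses inference on all of them. The primary objective covers all three doses, so the probability that all three succeed is a natural quantity to look at, although the protocol makes no power claim for it.

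**Working it through.** **Inputs.** Difference 0.5, SD 1.2, two-sided level 0.019, 90% power, 153 evaluable and 161 randomised per arm, 5% non-evaluable, 808 actually randomised (6.5); 1:1:1:1 allocation (3.1); three comparisons, each with placebo only (6.4.1). Equal arms sharing one placebo group give a correlation of 0.5 between the three test statistics.

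**1. The plan's own figure.** n = 2 × SD² × (z₁ + z₂)² / difference² = 2 × 1.44 × (2.3455 + 1.2816)² / 0.25 = 151.6, so 152 by the normal approximation. The noncentral t gives power 0.898 at 152 and 0.9001 at 153. The stated 153 is reproduced. 153 / 0.95 = 161.05, and 4 × 161 = 644.

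**2. Critical values.** For k comparisons, solve 1 − ∫ φ(u) [Φ(u + √2·c) − Φ(u − √2·c)]ᵏ du = 0.05.

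| k | critical value c | two-sided level |
|---|---|---|
| 3 | 2.349 | 0.0188 |
| 2 | 2.212 | 0.0270 |
| 1 | 1.960 | 0.0500 |

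With t quantiles (608 df) the k = 3 level is 0.01885. The plan's approximate 0.019 is this number rounded to three decimals.

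**3. Power per dose, single-step.** At 153 per arm the expected z is 0.5 / (1.2 × √(2/153)) = 3.644. At level 0.019, power is Φ(3.644 − 2.3455) = 90.3%; at 0.0188 it is Φ(3.644 − 2.349) = 90.2%. At the enrolled size, 808 / 4 = 202 and 202 × 0.95 = 191.9, so about 192 evaluable per arm; the expected z is 4.082 and power at 0.0188 is 95.8%.

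**4. Single-step against step-down.** Normal approximation, correlation 0.5, by simulation; repeat runs agree to within about 0.2 points.

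| Evaluable per arm; true differences | Quantity | Single-step at 0.019 | Single-step at 0.0188 | Step-down |
|---|---|---|---|---|
| 153; 0.5 / 0.5 / 0.5 | each dose | 90.3% | 90.2% | 94.1% |
| | all three | 78.7% | 78.6% | 88.5% |
| 192; 0.5 / 0.5 / 0.5 | each dose | 95.9% | 95.8% | 97.9% |
| | all three | 90.1% | 90.0% | 95.5% |
| 153; 0.3 / 0.4 / 0.5 (assumed) | weakest dose | 43.6% | 43.5% | 56.3% |
| | all three | 37.2% | 37.1% | 52.6% |
| 153; one dose 0.5, others 0 | active dose | 90.3% | 90.2% | 90.4% |

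The probability of at least one rejection is the same under both forms at the same first level, because the first step is identical.

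**5. Family-wise error of step-down at 153 per arm, active doses at 0.5.** Three true nulls 5.0%, two 4.7%, one 4.3%.

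**6. Effect on the hierarchy.** The most lenient level at which any dose can be declared significant on HbA1c is 0.05. The chain within a dose therefore still starts at no more than 0.05, and the within-dose control claimed in 6.2 is kept.

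**The case against.** The strongest reply is that nothing here is wrong. Single-step Dunnett is valid, the trial is sized for it, and it delivers the power promised for each dose. That stands, and the point is put as an improvement only. It is also true that the 153-per-arm gains overstate the case for the trial as enrolled: at about 192 per arm and true differences of 0.5, the gain per dose is about 2 points and for all three doses about 5.5 points. The graded pattern 0.3 / 0.4 / 0.5 is an assumption that no section of the protocol supports.

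Three stronger readings are tempting, and the document does not support them.

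- **That the plan exceeds 5% family-wise error.** A literal cutoff of 0.019 for all three tests gives 5.04%. But 6.2 and 6.5 say approximately 0.019 and tie it to Dunnett's method at 0.05 overall, so a Dunnett test run as named uses 0.0188 and holds 5%. The bare 0.019 later in 6.2 says when the secondary tests are performed. It is a wording matter worth 0.04 percentage points.
- **That the plan breaks its own promise of closed testing.** That description (synopsis and 2.2) concerns the order from primary to key secondary objectives, not the three dose comparisons.
- **That 2.5 mg is the dose set to fail.** Appendix I, section 4, reports a 24-week study in drug-naïve patients where a significant effect "was observed for the 5 and 10 mg dapagliflozin groups versus placebo". The same section reports significance for all three doses as add-on to metformin, and Appendix I, section 2, reports it for every dose group in the Phase 2b study. These results do not single out 2.5 mg.

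A last objection concerns timing. This edition already records 808 randomised patients, and the text does not show whether the 24-week data had been unblinded. The change is legitimate only before that, and should rest on the power argument rather than on sister-study results.

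**Conclusion.** The point holds as a cheap efficiency improvement. Sections 6.2 and 6.5 fix a valid but less powerful test. Step-down Dunnett keeps strong 5% control of the three primary hypotheses and rejects every dose that single-step rejects. Under the plan's assumptions (difference 0.5 for every dose, SD 1.2) the gain at 153 per arm is about 4 points per dose and 10 points for all three doses. At about 192 per arm it is about 2 and 5.5 points. It is larger for a weaker dose when the others work (about 13 points in the assumed graded pattern) and practically nil when only one dose works. These figures rest on the normal approximation and equal arms. The sample size and its 90% power stand.

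**What to change.** Before the 24-week treatment codes are opened:

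- In 6.2 and 6.4.1, specify step-down Dunnett on the three ANCOVA contrasts with placebo. Order them by |t|; test the largest at the three-comparison level (about 0.0188), the next at the two-comparison level (about 0.0270) and the last at 0.05; stop at the first non-significant result.
- State the decision rule as a step-down Dunnett-adjusted p-value of at most 0.05, and put that in place of the bare 0.019 in the later part of 6.2.
- Keep the key secondary hierarchy within each dose at 0.05, and align the reference to a global error rate in 6.2 with that scope.
- Leave 6.5 as it is; it becomes conservative.

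The cost is a few lines of text, with no extra patients or data, provided the amendment precedes unblinding. The drawback is that step-down Dunnett has no simple matching simultaneous intervals. The plan already reports ordinary 95% intervals, so nothing planned is lost; single-step Dunnett intervals can be shown alongside if wanted.

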- Change in seated systolic BP and seated diastolic BP from baseline to week 104, and from week 48 to week 104 in patients with baseline seated systolic BP > 140 mmHg
- Percent change in total cholesterol (TC), low density lipoprotein cholesterol (LDL-C), high density lipoprotein cholesterol (HDL-C), triglycerides (TG) and free fatty acids (FFA) from baseline to week 104, and from week 48 to week 104

Patient reported outcomes

(PROs) (not applicable)

Health economics (not applicable)

Pharmacokinetics

Plasma samples for analysis of dapagliflozin will be obtained at the Week 8 and Week 20 visits immediately prior to dosing, 60 minutes post-dose and 180 minutes post dose.

Genetics

Blood samples will be taken from patients who separately consent to optional blood sampling donation for deoxyribonucleic acid (DNA) analysis. The purpose is to enable future pharmacogenetic research studies. DNA collected from the samples and health information collected from the main clinical study may be used to investigate the effects of DNA variation on response to study treatments and the causes and further progression of type 2 diabetes and other metabolic diseases. Samples from this and other clinical studies may also be used in conjunction to accomplish these objectives. The samples will be destroyed after 15 years.

Statistical methods

The primary outcome variable, change from baseline to week 24 in HbA1c, will be analyzed by an analysis of covariance model (ANCOVA) which will be used to derive least squares estimates of the treatment differences (each dapagliflozin dose group versus placebo) in mean change with corresponding p-values and two-sided 95% confidence intervals. A hierarchical closed testing procedure will be used to control the Type I error rate across the primary and key secondary objectives. Efficacy will primarily be evaluated using the full analysis set.

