Patients with type 2 diabetes on at least 30 IU of insulin per day for at least 8 weeks prior to enrolment, with or without OADs with known HbA1c values $\geq 7,5\%$ and $\leq 10,5\%$ will provide informed consent and submit laboratory samples. Patients on metformin therapy should be on at least 1500 mg/day of metformin or at the maximum tolerable dose for a period of at least 8 weeks prior to enrolment. Patients on other OAD medications should be on at least half maximum daily recommended dose of the OAD for a period of at least 8 weeks prior to enrolment. Patient will be provided with a glucometer and a patient diary and be instructed to record their daily SMBG as well as insulin use during the next two weeks. Patients will be instructed to continue their current insulin and if applicable any ongoing OAD therapy at the same dose level during enrolment period.

24-week double-blind treatment period (Visit 2–9; week 0 to week 24)

If all lab inclusion criteria for V1 are met, Visit 2 should occur two weeks after visit 1. All further applicable inclusion and exclusion criteria will be checked and the mean daily insulin dose will be calculated by the investigator. The calculated mean daily insulin dose is an average total daily insulin dose used over the last seven documented days. Eligible patients with at least 30 IU calculated mean daily insulin dose will be randomized if the daily insulin requirements over the past seven days with insulin dose documentation does not vary more than 10% of the calculated mean daily insulin dose on more than one occasion. (For example for a patient whose calculated mean daily insulin dose is 50 IU, daily doses may not be <45 and >55 IU on more than one occasion within the past seven days with insulin dose documentation).

Eligible patients will be randomized in a 1:1:1:1 ratio to receive either dapagliflozin at 2.5 mg, 5 mg, 10 mg or placebo once daily. Patients will return for visits 1 week after start of treatment and then approximately every 4 weeks to assess efficacy and safety of the treatment. The patients will be instructed to record their fasting SMBG as well as insulin use daily. The patients will further be instructed to always self-monitor plasma glucose in case of symptoms suggestive of hypoglycaemia and to register any signs of hypoglycaemia in the supplied diary. During the study treatment the patients will be instructed to keep their insulin (and if applicable OAD) dose unchanged.

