6.4 Method of statistical analysis

6.4.1 Analysis of primary and secondary efficacy for the 24-week treatment period

The primary and secondary efficacy analyses will be based on the full analysis set. The primary endpoint may also be analyzed with the per-protocol analysis set. Treatment effects will be determined through pair-wise treatment group comparisons: each dapagliflozin treatment group versus placebo. No statistical comparisons will be made amongst the dapagliflozin groups.

For endpoints not examining insulin dose, the last post-baseline measurement prior to the first up-titration will be used for subjects whose insulin dose is up-titrated (i.e., patients are censored at the time of up-titration). Endpoints examining insulin dose will also use LOC, but without censoring at the time of titration. To directly assess the relationship between changes in insulin dose and HbA1c, changes in HbA1c will also be summarized using the observations from the same time points as analyzed for insulin dose as a supportive analysis.

The change from baseline to week 24 in HbA1c will be analyzed using an analysis of covariance model (ANCOVA) with factors for treatment group and use of other OADs as fixed effects, and covariate for baseline HbA1c. The model will be used to derive least squares estimates of the treatment differences (each dapagliflozin dose group versus placebo) in mean change with corresponding p-value and two-sided 95% confidence interval. Further, two-sided 95% confidence intervals for the mean change within each treatment group will be calculated.

To preserve the Type I error rate ≤ 0.050 (two-sided) across the primary and within each dose group for the four key secondary endpoints, a hierarchical step-wise procedure will be used to interpret the statistical significance of these treatment comparisons. The details of the step-wise procedure are provided in Section 6.2.

Continuous secondary efficacy variables will be analyzed by means of an ANCOVA for change from baseline using treatment group and use of other OADs as fixed effects and baseline value as a covariate. By analogy to the primary efficacy variable, the model will be used to derive point estimates and two-sided 95% confidence intervals for the mean change within each treatment group as well as for the difference in mean change between the dapagliflozin and placebo groups. Nominal p-values for the difference between the treatment groups will be provided.

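### Key secondary endpoints are error-controlled only within each dose, so the protocol's unqualified statements of closed and global Type I error control overstate what the procedure delivers across the three doses

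*Protocol*

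**What the plan says.** Section 6.2 of the protocol tests the change in HbA1c at week 24 for three doses against one placebo group by Dunnett's method, with an overall level of 0.05: "The significance level for each pair-wise group comparison of dapagliflozin versus placebo will be approximately 0.019".

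The four key secondary endpoints (body weight, absolute insulin dose, proportion with insulin dose reduction, FPG) follow in fixed order. The gate is applied dose by dose: "Only those dapagliflozin groups significantly superior to placebo for the primary outcome variable will have statistical inference versus placebo for the first key secondary outcome". Each later step depends on the one before. Section 6.2 gives the purpose as "to control the type I error rate within each dapagliflozin group at the 0.05 level". Section 6.4.1 has the same scope: "To preserve the Type I error rate ≤ 0.050 (two-sided) across the primary and within each dose group for the four key secondary endpoints".

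Two other statements carry no such limit. The synopsis, under Statistical methods, says: "A hierarchical closed testing procedure will be used to control the Type I error rate across the primary and key secondary objectives". The end of section 6.2 says that significance of the secondary comparisons is interpreted step-wise "in order to protect the global type I error rate of the hierarchical testing procedure".

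**The concern.** For the primary, the plan recognises that three doses give three chances of a false positive, and it pays for this by testing each at about 0.019. At the first key secondary step that payment stops. Every dose that passes starts its own sequence, and each sequence may spend up to 0.05. No section describes an adjustment across doses from that step on.

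A closed procedure, or one said to protect a global error rate, is normally understood to control the chance of any false rejection over the whole family. Here the family is 3 doses × 5 endpoints = 15 hypotheses. Three parallel sequences at 0.05 do not control that. The secondary objectives say that the hierarchy is there to support superiority claims for each dose, and section 3.6.2 ties the 24-week analyses to registration. A reader who relies on the synopsis would credit the secondary claims with more protection than they have.

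**Working it through.** **Inputs from the protocol**
- Dunnett, overall 0.05, about 0.019 per comparison (6.2).
- Key secondary sequence at 0.05 within a dose (6.2, 6.4.1), two-sided (6.4.1).
- Equal allocation to four arms (3.1). Two dose-placebo differences that share a placebo arm of equal size have correlation ρ = 0.5.
- Difference 0.5%, SD 1.2%, 153 evaluable per group, 90% power at 0.019 (6.5).

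**Assumptions**
- Each key secondary is tested at two-sided 0.05. No section gives the level of a single key secondary test; this is the natural reading of 6.2.
- Large-sample normal statistics.
- Correlation between endpoints of 0 to 0.5. The protocol gives none, so the range is shown.

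**Step 1: reproduce the plan's own figures.** For k comparisons at two-sided level α with critical value c, the chance of at least one false rejection is

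FWER = 1 − ∫ [Φ((c − √ρ·y)/√(1−ρ)) − Φ((−c − √ρ·y)/√(1−ρ))]^k φ(y) dy.

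With k = 3 and ρ = 0.5, FWER = 0.05 at α = 0.0188, and α = 0.019 gives 0.0504. This agrees with the stated 0.019. A two-sample t test with 153 per group has power 0.900, also as stated.

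**Step 2: the same formula at the key secondary level, body weight null in every dose that passes**

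| Case | Chance of at least one false key secondary rejection |
|---|---|
| Three doses, α = 0.05, ρ = 0.5 | 0.125 |
| Two doses, α = 0.05, ρ = 0.5 | 0.091 |
| Three doses, independent: 1 − 0.95³ | 0.143 |
| Three doses, only errors favouring dapagliflozin (one-sided 0.025), ρ = 0.5 | 0.063 |

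**Step 3: the full gated procedure by simulation** (400,000 trials per case; primary at 0.019 per dose, then four key secondaries in fixed order within the dose). The two values are for between-endpoint correlation 0 and 0.5.

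| Case | Secondaries at 0.05 | At 0.019 | At 0.0167 |
|---|---|---|---|
| Primary certain to pass, weight null in all doses | 0.127, 0.125 | 0.051, 0.050 | 0.044, 0.044 |
| Primary with 90% power per dose, weight null in all doses | 0.114, 0.101 | 0.046, 0.038 | 0.041, 0.033 |
| First true null on a different endpoint in each dose | 0.142, 0.138 | 0.057, 0.055 | 0.049, 0.048 |
| Every null true, primary included | 0.050, 0.050 | 0.050, 0.051 | 0.051, 0.051 |

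In the last row the primary gate alone sets the rate. It equals 0.0504 whatever the secondary level, and the small differences are simulation error.

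**Step 4: what a strict 5% takes.** Within a dose, a fixed sequence at level α throughout has error at most α. If primary and key secondaries both use 0.05/3 = 0.0167, the sum over three doses is at most 3 × 0.0167 = 0.05 under any correlation. If the primary stays at 0.019 and only the secondaries move to 0.0167, the bound fails slightly. Two doses with a null primary give 0.0356. Adding one dose with a null secondary on an uncorrelated endpoint gives 1 − (1 − 0.0356)(1 − 0.0167) = 0.0517.

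**Step 5: power cost.** A test with 90% power at two-sided 0.05 has noncentrality 1.960 + 1.282 = 3.242. At 0.019 its power is Φ(3.242 − 2.346) = 0.81, and at 0.0167 it is Φ(3.242 − 2.394) = 0.80. For the primary, the noncentrality is (0.5/1.2)·√(153/2) = 3.644. Moving it from 0.019 to 0.0167 takes power from Φ(3.644 − 2.346) = 0.903 to Φ(3.644 − 2.394) = 0.894.

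**The case against.** The strongest reply is that dose-wise control is a disclosed choice. Sections 6.2 and 6.4.1 say openly that the key secondaries are controlled within a dose, and the gated fixed sequence delivers that. Claims are framed for each dose, no comparisons between doses are made, and the primary is adjusted across doses. The synopsis can be read as meaning across endpoints, and the global rate in 6.2 as that of the procedure just defined as within-dose.

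Much of this stands. A reader might infer that the protocol promises 5% for the key secondaries over all doses and that the true rate is more than double the promise. The documents do not support that: every 0.05 attached to the key secondaries is limited to one dose group. A reader might also take 12.5% as the rate of false superiority claims. It counts two-sided rejections, including those where dapagliflozin is worse; in the favourable direction the rate is 6.3%. The inflation also needs at least two doses to pass the primary while key secondary nulls are true.

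What does not stand is that the wording is harmless. Neither broad statement names a dose, both concern confirmatory claims, and the procedure lacks the property they describe. Several doses passing HbA1c is also what the trial is designed to show, so the condition for inflation is not remote.

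**Conclusion.** The point holds as an inconsistency of scope. The primary is controlled across the three doses; the key secondaries are controlled at 0.05 only within each dose; the synopsis and the end of section 6.2 describe broader control than that.

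With two-sided 0.05 tests, the chance of at least one false key secondary rejection across doses is about 12.5% when all three doses pass and body weight is null in all. It is about 9% with two such doses, 10–11% with 90% primary power per dose, and up to about 14% when the first true nulls lie on different endpoints. In favour of dapagliflozin only, it is about 6.3% in the three-dose case, against 2.5% for a single such test. Under the complete null it is about 5%.

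These figures rest on the inferred 0.05 per test, ρ = 0.5 from equal allocation, and the assumed range of between-endpoint correlation. The primary conclusion, its significance level and the sample size are not affected.

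**What to change.** Choose one of two routes before unblinding.

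(a) If dose-wise control is intended, limit the synopsis statement and the global wording in section 6.2 to control within each dose group. State the across-dose rate (about 12.5% two-sided when all three doses pass and weight is null in all) and present the secondary claims as dose-wise. This costs wording only.

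(b) If control over all doses is intended, state in sections 6.2 and 6.4.1 that each dose carries its own primary level down its sequence. At 0.019 the rate is about 5.0% with weight null in all doses and about 5.6–5.7% in the worst case run. For a guaranteed 5%, use 0.05/3 = 0.0167 per dose for both the primary and the key secondaries; lowering only the secondaries is not quite enough. The price is key secondary power: a test with 90% power at 0.05 keeps about 81% at 0.019 and about 80% at 0.0167. Moving the primary to 0.0167 as well takes its power at 153 per group from about 90.3% to 89.4% (normal approximation).
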